#### 8.0 REMOVAL FROM PROTOCOL AND OFF-STUDY CRITERIA

The survival for all participants will be followed on study until their death unless they or their parents request that no further information be made available to this study group.

For participants who are treated at collaborating institutions it is recommended that each patient to be taken off protocol be discussed with the PI of the study and if needed, pertinent studies should be sent to the PI for review.

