#### 8.1 **Off-Study Criteria**:

- Parent/Patient request
- Death
- PI discretion
- Lost to follow-up
- Protocol compliance
- Study completion
- Treatment with chemotherapy during the administration of radiation therapy
- Disease progression

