#### 11.1 **Statistical Analysis of Primary Objective 1.1**

The primary objective is to estimate the distributions of PFS and OS post reirradiation at initial failure for patients with ependymoma. In addition, we will monitor PFS as compared with the retrospective historical data discussed in section 11.0 to ensure that the current approach is not inferior to the retrospective historical experience.

Based on the work of Korn and Freidlin (2006) [297] we will estimate the sample size required to monitor that the prospective results are not inferior to the retrospective results, as if a prospective randomized trial were to be conducted. The historical PFS data were used to estimate the hazard rate during the first 4 years of 0.233 and for the hazard rate for the period greater than 4 years of 0.056. The following figure shows that a piece-wise exponential distribution with these two hazard rates is an outstanding fit to the historical PFS distribution.

The calculations for the monitoring design assume piece-wise exponential distributions. The design will have 80% power to detect an unacceptable decrease in the 3-year PFS rate from 50% to 35% ( $\alpha$ =0.10: one-sided test). East© (version 5) was used to calculate that with one interim analysis and approximately 64% of patients assigned to the new treatment, a total of 140 patients would need to be

IRB Approval date: IRB APPROVAL DATE: 02/01/2023 randomized over 9 years of accrual. Thus, we will need to accrue 90 patients to our new regimen over approximately 9 years. The final analyses will be conducted 2 years after initiation of irradiation for the last patient.

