also use the information recorded in the clinical neurology form (see appendix) and NCI CTCAE v4.0 when relevant. The percentages for both statuses will be estimated. Generalized Estimating Equations (GEE) with logistic link will be employed to estimate the change of vision over time, and compare severity of vision in the two treatment groups adjusted by confound factors.

**Audiology:** To assess hearing loss in patients, hearing will be dichotomized as normal if all thresholds are within 0-20 DB HL and otherwise abnormal. GEE with logistic link will be modeled to explore the trend over time and investigate impacts of specific clinical and treatment factors on hearing loss. In the presence of missing data, Weighted GEE will be employed to address missingness. In addition, the cumulative incidence of hearing loss will be estimated with death as a competing risk. Chang Ototoxicity Grading Scale (COGS) will also be used to evaluate the hearing loss. The ordinal COGS will be analyzed similarly as Neurology grade.

**Endocrine:** Endocrine data as a continuous variable will be collected. Descriptive statistical analysis will be performed. Diabetes Insipidus (DI) is a hormone deficiency that results only from direct damage to the hypothalamus and pituitary axis (mainly pituitary stalk) by tumor or surgery. This longitudinal binary variable (coded as "yes" or "no") will be compared between the surgery and radiation groups using GEE adjusted by other confounding factors. Hormone Deficiency, such as Growth Hormone Deficiency (GHD), will be compared between the surgery and radiation groups. Growth hormone will be dichotomized with GHD=1 for <7ng/ml and GHD=0, otherwise. We define GHD=1 as event. Since the treatment of other hormone deficiency could be a compete risk for this event, cumulative incidence regression analysis using Fine and Gary method will be employed [301]. Specific clinical and treatment group factors will be included as covariates to investigate the treatment group difference. Other Hormone Deficiency, including Thyroid Hormone Deficiency (central hypothyroidism), Adrenal Insufficiency, Gonadotropin Deficiency or Precocious Puberty, Diabetes Insipidus, Hypothalamic Obesity (not a specific endocrine deficiency but an endocrine problem nonetheless), will be analyzed similarly. Some of these measures are graded in the NCI CTCAE v4.0.

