**Neurocognitive:** Neurocognitive measures are continuous. GEE will be employed to estimate treatment group difference with specific clinical factors and time also included as covariates. For some neurocognitive measures, children and young adults (adolescents) will have different forms. When we pool data together to perform the analysis, we will take these differences into account in the GEE model to control for variations. Neurocognitive measures will also be dichotomized into normal and abnormal groups based on cut-off values (average range vs. outside of the average range for a given test instrument) at specific time points after therapy. GEE with logistic link will be used to investigate the treatment group effect. Frequency and percentage of dichotomized cognitive measures will be calculated.

St. Jude Children's Research Hospital IRB NUMBER: Pro00004349

IRB APPROVAL DATE: 02/01/2023

IRB Approval date:

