As an exploratory analysis, each of above mentioned measurements will be compared between two treatment arms by longitudinal data analysis. Generalized Estimating Equation (GEE) will be employed to compare outcome changes over time between two treatment arms by using time and treatment as covariates of the model. The interaction term between treatment arm and time will be added if two arms show different change rate. The other covariates of interest will be selected by Bayesian information criterion (BIC). However, any response with <3 assessments would not be included in the list. To analyze sleep measurements which will be examined annually, the other measurements used in the model will only include their data points measured at the same time as sleep measurements. Multidimensional Fatigue scale and Peds brain tumor module will be measured each week for 4 weeks at the first year. We will analyze them in two ways. First, we will only use the first 4 weeks data to fit the GEE. Second, it will also be fitted in a large time picture but only the first week data of these 4 weeks will be used. In addition, Epworth Sleepiness Scale score will also be dichotomized by 10 and then fitted using GEE with a logistic link.

Similarly, the same modeling approach will be used to explore associations between each of above mentioned outcome and patient characteristics/clinical

St. Jude Children's Research Hospital

IRB NUMBER: Pro00004349
IRB APPROVAL DATE: 02/01/2023

factors that are of interest. The independent effect of resultant significant factors will be explored further in multiple regression models.

Based on the number of tests performed to address this secondary objective, adjustments for multiple comparisons will be made to mitigate over interpreting exploratory findings.

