# 11.4 Statistical Analysis of Secondary Objective 1.2.3 Physical Performance

Objective: To describe physical performance and movement in children, adolescents and young adults with ependymoma treated with a second course of radiation.

Physical performance measures will be obtained at baseline, 12, 24, 36, 48 and 60 months. We will provide descriptive statistics of the following outcomes at each time point, and also provide the plots of individual profiles and mean profiles of the outcomes across time. The descriptive statistical analysis will be stratified by gender, age at diagnosis and total dose of brain radiation.

To model the outcomes' pattern and change over time, we will use generalized estimating equation (GEE) methodology with time as the main independent variable while adjusting for gender, age at diagnosis and total dose of brain radiation, including an interaction term if indicated. The assigned distribution and link function in each model will depend on the characteristic of the specific outcome as listed in next paragraph(s). The continuous measures will be modeled using normal distribution and identity link whereas the binary outcomes will be modeled using binomial distribution and logit link.

These analyses will be conducted at the conclusion of the trial and at an interim time point at which we have 15 patients in each stratum (a total of at least 45 patients) followed for 1 year. The results of the interim analyses will be submitted for presentation at an appropriate national scientific meeting, as well as to the CT-SRC.

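### Neurocognitive, sleep/quality-of-life and physical outcomes are planned with unweighted GEE and no missing-data method, although about half of patients are expected to leave testing through progression or death by year 3

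*Combined protocol and SAP*

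**What the plan says.** Section 11.2, Neurocognitive: "GEE will be employed to estimate treatment group difference", with time and clinical factors as covariates. A dichotomized version uses GEE with a logistic link. Vision and diabetes insipidus in the same section are also analysed by GEE.

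Section 11.3: "Generalized Estimating Equation (GEE) will be employed to compare outcome changes over time between two treatment arms".

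Section 11.4: "we will use generalized estimating equation (GEE) methodology with time as the main independent variable", adjusted for sex, age at diagnosis and brain radiation dose.

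None of these paragraphs gives a missing-data method or a working correlation. The one exception among the GEE analyses is audiology in 11.2: "In the presence of missing data, Weighted GEE will be employed to address missingness". Neurology grade, the Chang hearing grade and neuroimaging (11.5) use mixed-effects models, and hormone deficiency uses a competing-risks regression.

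The off-study list in section 8.1 includes "Disease progression". What continues afterwards is stated in section 8.0: "The survival for all participants will be followed on study until their death". Nothing says that functional testing continues after progression. Section 6.6.1 schedules cognitive testing yearly to year 5.

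**The concern.** Unweighted GEE uses whatever visits are observed. It is generally consistent for the full-cohort trajectory only if, given the covariates in the model, the chance of being observed does not depend on the outcome. Here the main reason for a missing late visit is progression or death. If function before progression predicts progression, patients seen at years 3 to 5 are a selected group, and the fitted trend mixes change within patients with the loss of the worse performers.

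The covariates may not absorb this. Section 11.4 omits pattern of failure, extent of resection and recurrent histology, all of which the historical analyses in section 11.0 associate with PFS or OS.

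This matters because section 2.3 says that cognitive monitoring could bear on whether the treatment is acceptable. The plan names a remedy but applies it to one outcome.

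**Working it through.** **1. How much dropout to expect.** Section 11.1 gives a historical PFS hazard of 0.233 per year for years 0-4 and 0.056 afterwards.

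- Year 3: S(3) = exp(-3 × 0.233) = 0.497, which reproduces the stated 50%.
- Check from the yearly counts in Table 11.1: (1 - 13/48.5)(1 - 5/33)(1 - 5/25) = 0.497, against the tabulated 0.500.
- Year 5: S(5) = exp(-(4 × 0.233 + 0.056)) = 0.372. Table 11.1 itself gives 0.402.
- Design alternative (35% at 3 years): hazard ratio = ln 0.35 / ln 0.50 = 1.515, applied to both hazards.

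Expected progression-free patients out of 90:

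| Year | 1 | 2 | 3 | 4 | 5 |
|---|---|---|---|---|---|
| Historical hazards | 71.3 | 56.5 | 44.7 | 35.4 | 33.5 |
| Design alternative | 63.2 | 44.4 | 31.2 | 21.9 | 20.2 |

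So 50% (historical) to 65% (alternative) have progressed or died by year 3, and 63% to 78% by year 5.

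**2. What that dropout could do to GEE.** The documents give no data on the link between function and progression, so this step is illustrative. Assumptions: 400,000 simulated patients; yearly visits 0-5; two equal groups with slopes of -2 and -3 points/year (average -2.50, difference -1.00); intercept SD 13, slope SD 2, residual SD 6; dropout matched to the hazards above; exchangeable correlation fixed at 0.75. In the random and observed-score cases the weights use the true dropout probabilities, which is a best case. Pairs are for log-odds of 0.5 and 1 per SD; single values for the reversed links are for 0.5.

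| Dropout depends on | GEE, independence | GEE, exchangeable | Weighted GEE |
|---|---|---|---|
| Nothing (random) | -2.50 | -2.50 | -2.50 |
| Lower last score | -1.34, -0.56 | -2.33, -2.19 | -2.50, -2.44 |
| Greater decline from baseline | -2.24, -2.03 | -2.30, -2.13 | -2.50, -2.49 |
| Higher last score | -3.67 | -2.68 | -2.51 |
| Smaller decline | -2.77 | -2.70 | -2.51 |
| Unobserved steeper slope | -1.71, -1.24 | -1.82, -1.40 | -1.65, -1.15 |

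In the last row the weights see only the overall dropout rate.

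**3. The group difference in slope (true -1.00).** With similar dropout in both groups, unweighted GEE gave -0.87 to -1.01 over all rows. With dropout depending on decline and also higher after craniospinal irradiation (log-odds 0.7), it gave -0.86 (independence) and -0.89 (exchangeable); weighted GEE gave -0.99. The worst error is therefore 14%, against (2.50 - 0.56)/2.50 = 78% for the overall slope.

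**4. Limits of the remedy.** In smaller runs with dropout driven by an unobserved slope (true slope -2, slope SD 2, hazard multiplied by 1.65 per SD of worse slope), a mixed model recovered only -1.44. Weights built from prior score and change gave -1.29 to -1.47, against -1.27 to -1.33 for unweighted exchangeable GEE in the same runs.

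**The case against.** A reader might infer that late effects will be understated. The documents do not support that. No section reports whether function before progression predicts progression. Random dropout gives no bias, and the opposite link reverses it. With an exchangeable working correlation, the understatement when observed worse function predicts dropout was 7% to 15% (-2.33 to -2.13 against -2.50). This objection stands, and it limits the point to a possible bias whose probable direction is an inference.

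The planned contrast in 11.2 and 11.3 is between treatment groups. Treatment is in the model, so unequal dropout between groups is not in itself a bias, and the simulated group difference was affected little. This also stands. The point bears mainly on time trends, which are the main target in 11.4.

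Decline after progression mixes tumour, later therapy and re-irradiation, and function after death is undefined, so function while progression-free is a legitimate target. That is correct, but the plan does not choose it. The average among patients still progression-free at each visit describes a shrinking, selected group. The rate of change over progression-free time, averaged over all treated patients, is a different quantity, and unweighted GEE need not estimate it.

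A reader might also infer that weighting cures the problem. It does not if dropout follows unobserved decline.

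Finally, these are secondary, largely exploratory analyses with no power claim. That lowers the weight of the point but does not remove it.

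**Conclusion.** The gap is real. GEE is planned without a missing-data method for neurocognitive, vision, diabetes insipidus, sleep/quality-of-life and physical outcomes, while audiology alone gets weighted GEE. About 45 of 90 patients are expected to be progression-free at year 3 and 34 at year 5. These are historical rates, not rates observed in the trial, and they rest on reading sections 8.0 and 8.1 as ending functional testing at progression.

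Time trends may be biased, probably toward understating decline if worse observed function goes with earlier progression. In the simulation the size ran from nil to 78% of the true slope. It depended on the dropout link and on the working correlation, which the plan does not state. Under the same assumptions the focal-versus-craniospinal difference was off by at most 14%. Confidence is high that the method is under-specified; direction and size remain assumptions. This is worth correcting, but it does not affect the primary objective.

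**What to change.** For the longitudinal outcomes in 11.2-11.4 that are analysed by GEE:

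1. State the estimand, for example function while alive and progression-free, and say whether it is averaged over all treated patients or over those still under observation at each visit. If the latter, label it so and weight only for missed tests among those patients.
2. For trajectories meant to represent all treated patients, extend the weighted GEE already planned for audiology, with weights from prior scores, treatment stratum and prognostic factors. Alternatively, use a likelihood-based mixed model with random slopes. State the working correlation or covariance. For binary outcomes, weighted GEE keeps the population-average meaning.
3. Say that both methods assume data missing at random. Add one sensitivity analysis for dropout not at random, for example a joint model for IQ and progression, and report it as such.

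The cost is a little more analysis work and somewhat wider intervals from weighting. No new visits or data are needed.

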#### 2.3 Psychology Studies and Neurocognitive Outcomes

Children who receive radiation therapy for ependymoma are at increased risk for impairments in cognitive functioning [19]. There is strong evidence to suggest that total radiation dose and volume of irradiated brain play a significant role in cognitive outcomes, with lower doses of cranial radiation associated with less intellectual impairment [20, 21]. Given this finding, it is predicted that reirradiation may be associated with additional cognitive morbidity; thus, it is imperative that cognitive outcomes be closely monitored. Cognitive monitoring conducted within the context of this protocol could significantly impact determinations regarding the acceptability of this treatment approach.

A progressive decline in intellectual functioning (IQ) after radiation therapy for childhood brain tumors has been well-established [22-25]. Increased utilization of special education services has also been reported and cranial irradiation has been associated with poor academic performance on standardized measures in childhood brain tumor survivors [21, 23, 26, 27]. Further, studies have found declines in academic functioning for children 2 to 5 years after irradiation [28, 29]. Previously reported findings from the RT-1 protocol indicate that reading, in particular, may be more vulnerable than other academic skills and may decline despite stable intellectual functioning in children treated for ependymoma with conformal radiation therapy [30].

More recently, research investigators have tried to identify specific cognitive deficits that may underlie global declines in intellectual function or academic achievement. Reports of deficits in attention [31], working memory (online maintenance and manipulation of information) [32], and processing efficiency [33] are most prevalent. These emerging areas of core deficit are informative as nearly half of age-related improvements in IQ can be accounted for by developmental improvements in working memory and processing speed [34]. Accordingly, these cognitive domains will be the focus of serial monitoring.

Radiation therapy is a well-established cause of changes in cerebral white matter [35]. There is accumulating evidence to suggest that reduced cerebral white matter accounts for a significant proportion of the observed decline in IQ among

Rev. 3.2 dated: 1/19/2023 IRB Approval date: Protocol document date: 1/19/2023

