#### Memory Measures

California Verbal Learning Test, Children's Version (CVLT-C) [233]: The CVLT-C is a list-learning measure of verbal memory that includes five presentations of a list of 15 words comprising three categories. Learning is evaluated across the five learning trials as well as following a distracter list, short and long delays. Children are also presented with categorical cues and a list of target and non-target words from which they must identify those words presented on the 15 item list. Process scores allow evaluation of encoding, retrieval, retention and recognition abilities. The California Verbal Learning Test, Second Edition (CVLT-II) [234] is a comparable version of the test administered to individuals 17:0 years of age and older. It comprises sixteen words from four semantic categories and provides the same structure, allowing for the examination of encoding, retrieval, retention, and recognition. To reduce practice effects, this measure will only be administered at baseline, 2 years post and 4 years post. (15-20 minutes)

CogState [224, 225]: For the Continuous Paired Associate Learning task, the child is asked to learn and remember figures hidden beneath different locations on the screen. The shapes then appear centrally, and initially all appear peripherally for matching and remembering where each was located. Thereafter, as each picture is revealed centrally, they are required to tap the peripheral location that hides the same shape. Total errors is the outcome measure (~6 minutes).

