# 11.2 Statistical Analysis of Secondary Objective 1.2.1 Neurological, Endocrine and Cognitive

Objective: To explore potential associations of clinical and treatment factors with the incidence and severity of neurological, endocrine and cognitive deficits in children and young adults with ependymoma treated with a second course of irradiation.

To assess the side effects of radiation therapy in neurology, ophthalmology, audiology, endocrinology, and cognitive state, the data will be collected in a longitudinal setting. The time schedule for data collection is presented in Table 6.0.1 (Evaluations at baseline and follow-up). Since patients treated by focal or craniospinal radiation will be not at random, to compare the treatment effect, we need to adjust other clinical factors to limit the confound effects in the regression models as discuss below. In addition to the analysis plan below, once we have 15 patients in each stratum (a total of at least 45 patients) followed for 1 year, descriptive statistical analyses and regression analyses as discussed below will be conducted. The results of these interim analyses will be submitted for presentation at an appropriate national scientific meeting, as well as to the CT-SRC. There are not expectations that the findings of these interim analyses would raise concerns for the current trial.

**Neurology:** The neurologic signs and symptoms such as seizures, headache, motor sensation, ataxia, cranial nerve deficits and others will be collected. Neurological data will be obtained from the neurological protocol exam form. Grade 3-5 toxicity data as determined by the NCI CTCAE v 4.0 will be reported. The distribution of ordinal outcomes and percentages will be estimated. Mixedeffects Proportional Odds Regression [300] will be performed to estimate their changes over time, and compare severity in the two treatment arms adjusted by confound factors.

**Ophthalmology:** Vision status of a patient will be dichotomized into None and Impaired, according to clinical meanings, as described in Section 6.3. We will

St. Jude Children's Research Hospital IRB NUMBER: Pro00004349

IRB APPROVAL DATE: 02/01/2023

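### The supplementary binary neurocognitive outcome codes better-than-average scores as abnormal, although the objective concerns deficits

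*Combined protocol and SAP*

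**What the plan says.** The objective in section 11.2 concerns the "incidence and severity of neurological, endocrine and cognitive deficits" after a second course of irradiation. The neurocognitive paragraph starts from the scores as measured: "Neurocognitive measures are continuous. GEE will be employed to estimate treatment group difference with specific clinical factors and time also included as covariates". It then adds a binary version at specified times after therapy, in which the measures are "dichotomized into normal and abnormal groups based on cut-off values (average range vs. outside of the average range for a given test instrument". Two uses follow: "GEE with logistic link will be used to investigate the treatment group effect", and "Frequency and percentage of dichotomized cognitive measures will be calculated".

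No numerical limits for the average range are given, and no statement confines abnormal to one side of it. Section 6.6 and its Table 1 describe each instrument, its age range and its administration time, but give no cut-off and no scoring direction. Section 2.3 makes the expected direction of effect clear: "A progressive decline in intellectual functioning (IQ) after radiation therapy for childhood brain tumors has been well-established".

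**The concern.** A score above the average range lies outside it. On the plain wording, a child who reads or reasons better than average is therefore placed in the same category as a child with a deficit. If that child declines into the average range between annual follow-up tests, the code moves from abnormal to normal, so a loss is recorded as an improvement. In a group, losses from the upper tail offset gains in the lower tail. The abnormal rate then responds less to a true decline, or to a true difference between focal and craniospinal treatment, than a rate that counts deficits only.

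Section 2.3 says cognitive monitoring could bear on whether this treatment is judged acceptable. Section 11.2 also plans interim descriptive and regression results for a scientific meeting and for the CT-SRC. Percentages built on this rule could be presented there and read as rates of deficit.

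**Working it through.** The plan states no rate, power or sample size for this outcome, so there is no figure to reproduce. The check has a textual part and an illustration.

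**Text.** Set the rule beside its neighbours. The growth hormone cut-off in 11.2 is one-directional (event if below 7 ng/ml). So is the balance cut-off in 11.4 (below 70% marks fall risk). The neurocognitive rule names only inside and outside, and nothing in 6.6, Table 1 or 11.2 narrows it.

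**Illustration: inputs.** All are assumptions, because the documents give none of them:
- scores normally distributed, SD 15;
- average range 85–115, with 90–110 as an alternative;
- a true fall of 7.5 points (0.5 SD);
- higher scores are better;
- starting mean μ from 100 down to 85.

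**Formulas.** Below = Φ((85 − μ)/15). Above = 1 − Φ((115 − μ)/15). The rule as written counts below + above; a deficit rule counts below only. Share of signal lost = 1 − (change as written)/(change in below).

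**Example, μ = 100 falling to 92.5.** Below goes from Φ(−1) = 15.9% to Φ(−0.5) = 30.9%, a rise of 15.0 points. Above goes from 15.9% to 1 − Φ(1.5) = 6.7%. As written, abnormal goes from 31.7% to 37.5%, a rise of 5.8 points. Lost: 1 − 5.8/15.0 = 61%.

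Range 85–115 (losses computed from unrounded values):

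| Starting mean | Deficit side only | As written | Share lost |
|---|---|---|---|
| 100 | 15.9% → 30.9% | 31.7% → 37.5% | 61% |
| 95 | 25.2% → 43.4% | 34.4% → 46.7% | 32% |
| 90 | 36.9% → 56.6% | 41.7% → 58.1% | 17% |
| 85 | 50.0% → 69.1% | 52.3% → 69.8% | 9% |

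With 90–110 the shares lost at the same means are 72%, 47%, 30% and 20%. Each row can also be read as two treatment groups whose means differ by 7.5 points.

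**Above the norm the rule can fail completely.** With 85–115, a fall in mean from 105 to 95 leaves the abnormal rate at 34.4%. A fall from 110 to 100 lowers it from 41.7% to 31.7%.

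**Direction across the battery.** Replacing the rule with below average would not be right for every score. Table 1 describes the BRIEF as a measure of executive dysfunction, and section 6.6 describes the BASC-2 as combining clinical problem scales with adaptive scales. The unfavourable side has to be stated score by score.

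**The case against.** The strongest reply is that this is drafting shorthand. The objective is about deficits, and the audiology rule in 11.2 is written the same way (normal if within 0–20 dB HL, otherwise abnormal) although its purpose is plainly hearing loss. An analyst might code only the impaired side without being told. That is plausible, but no sentence says so, and the written rule classifies high scores as abnormal.

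A second reply concerns size, and most of it stands. These children have already been irradiated. Section 2.3 describes established IQ decline after radiation, and section 2.1 reports decline among assessed re-irradiated patients in an outside series. A cohort mean below 100 is therefore likely, and the loss shrinks as the mean falls. At a mean of 85 with the 85–115 range, only 2.3% of children are above the range against 50% below it.

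Three stronger readings are tempting, and the documents do not support them:
- *The plan would miss cognitive decline.* The continuous GEE comes first and does not depend on any cut-off; the binary analysis is an addition within an exploratory objective.
- *Baseline impairment would be overstated.* The dichotomy is specified for times after therapy. No baseline binary rate and no recovery endpoint is planned.
- *Every error count or symptom scale in the battery proves the mixed-direction problem.* For the paired-associate task, section 6.6 does say "Total errors is the outcome measure", but it also says CogState tasks receive age-based standard scores, so raw errors need not be what is classified. The BSI measures parental distress, not the child's cognition.

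**Conclusion.** The point holds as a fault in a written rule with limited reach. Followed literally, 11.2 counts better-than-average scores as abnormal and can code a post-therapy decline as a return to normal. Only the supplementary logistic GEE and the reported percentages are affected.

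The size cannot be fixed from the documents. Under the stated assumptions the loss of signal runs from about 61% for a cohort at the healthy norm to about 9% for one averaging 85 (range 85–115); a narrower average range makes it larger. A reader might take the 61% as the expected loss in this trial. It is not: it requires a previously irradiated cohort to start at the population mean, and the background sections suggest a lower one. The wording should still be corrected, because the repair is simple and the results may be presented while the trial is running.

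**What to change.** In 11.2, define abnormal as a score on the unfavourable side of the average range for that instrument: below the lower limit where higher is better, above the upper limit where higher is worse. State that scores better than the average range are coded normal.

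In Table 1, add the direction and the numerical average-range limit for each score to be dichotomized. Give separate entries for the BASC-2 clinical and adaptive scales, and an explicit direction for the BRIEF. The numerical limit matters as much as the direction: at the norm, the deficit-side rate is 15.9% with a lower limit of 85 and 25.2% with a lower limit of 90.

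The cost is a short change to 11.2 and two columns in Table 1. No data collection changes, and the continuous analysis stays as it is. Any percentages already produced under the present rule would need recoding from the stored scores.
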